12.2 Reporting of Adverse Events

Researchers will record the occurrence time, type, severity, handling measures, and outcome of adverse events in detail in the CRF. Mild and moderate adverse events will be reported to the study leader and the Ethics Committee within 24 hours; severe adverse events (such as death, severe allergy requiring emergency treatment, severe hypotension unresponsive to treatment) will be reported immediately (within 2 hours) to the study leader and the Ethics Committee, and a follow-up report will be submitted after the event is handled.

12.3 Handling of Adverse Events

For adverse events related to the study, researchers will take timely and effective medical measures to treat the subjects, reduce the impact of adverse events, and closely observe the recovery of the subjects. If the adverse event is severe and cannot be controlled, the subject will be withdrawn from the study, and follow-up medical treatment will be arranged to ensure the safety of the subject. For adverse reactions related to adenosine infusion during stress perfusion, infusion will be stopped immediately, and symptomatic treatment (such as fluid replacement, atropine administration for bradycardia) will be given.

13. Study Termination

1. Voluntary Termination: The study leader may terminate the study voluntarily if the study objectives are achieved in advance, or if serious safety problems, ethical issues, or other unexpected factors that affect the study progress occur during the study.
2. Termination by the Ethics Committee: The Ethics Committee may terminate the study if it finds that the study does not comply with ethical principles, or if the risks to the subjects exceed the benefits.
3. Termination Due to Other Reasons: The study may be terminated due to insufficient funding, difficulty in recruiting subjects (failure to reach the planned sample size within the scheduled time), or changes in national policies and regulations.
4. Disposal After Termination: After the study is terminated, the data collected will be sorted out and analyzed, and a study termination report will be written and submitted to the Ethics Committee and relevant departments. The follow-up of the subjects will be continued if necessary to ensure their safety and rights.

14. Study Team and Responsibilities

1. Principal Investigator (PI): Responsible for the overall design and implementation of the

study, coordinating the work of each research center, making important decisions related to the study, and ensuring the scientificity and ethicality of the study, especially the standardization of MVD assessment using stress perfusion CMR.

- 2. Co-Investigators: Responsible for subject recruitment, baseline assessment, follow-up, and data collection at each research center, ensuring the accuracy and completeness of MVD-related data and endpoint event records, and reporting adverse events and endpoint events in a timely manner.
- 3. Sub-Investigators: Assist the co-investigators in completing the study work, including data entry, sample collection, and follow-up visits.
- 4. Radiologists: Responsible for stress perfusion CMR image acquisition, image quality control, MVD assessment (based on MPR values), and LGE image review to exclude infarct patterns, ensuring the reliability of CMR and MVD data; briefly use AI software for auxiliary image feature extraction.
- 5. Data Managers: Responsible for data entry, verification, storage, and management, ensuring the confidentiality, integrity, and security of the data, with special focus on MVD-related indicators and endpoint event records.
- 6. Statisticians: Responsible for the design of the statistical analysis plan, statistical analysis of the study data (focusing on the correlation between MVD and SCD-related events), and providing technical support for the study results.
- 7. Study Coordinators: Responsible for the daily management of the study, coordinating communication between the research team and subjects, and ensuring the smooth progress of the study.
- 8. Ethics Committee: Responsible for reviewing the study protocol and informed consent form, supervising the ethical conduct of the study, and protecting the rights and interests of the subjects.
- 9. Endpoint Event Judgment Committee: Composed of 3 senior cardiologists, responsible for reviewing and confirming the occurrence of primary and secondary endpoint events, ensuring the accuracy and consistency of endpoint event judgment.

15. Investigator Official Titles

Role	Investigator Official Title
Principal Investigator	Principal Investigator, Department of Cardiology, [Hospital Name]; Chief Physician; Professor
Co-Investigator	Co-Investigator, Department of Cardiology, [Hospital Name]; Associate Chief Physician;

	Associate Professor
Sub-Investigator	Sub-Investigator, Department of Cardiology, [Hospital Name]; Attending Physician
Radiologist	Chief Radiologist / Cardiac Imaging Specialist, Department of Radiology, [Hospital Name] (proficient in stress perfusion CMR and MVD assessment)
Study Coordinator	Study Coordinator, Department of Cardiology, [Hospital Name]
Statistician	Statistician, Department of Biostatistics, [Hospital Name] / [Research Institute]

Appendix S1: Diagnostic Criteria for SCD-Related Events

1. Sudden Cardiac Death (SCD): Death due to cardiac causes occurring within 1 hour of the onset of acute cardiac symptoms, characterized by sudden loss of consciousness. For unwitnessed deaths with clear evidence of cardiac etiology, it is classified as probable SCD .
2. Appropriate Implantable Cardioverter-Defibrillator (ICD) Shock: Shocks delivered by an ICD in response to hemodynamically unstable ventricular tachycardia (VT) or ventricular fibrillation (VF) that is not caused by reversible factors (such as electrolyte imbalance, drug effects) .
3. Resuscitated Cardiac Arrest: A cardiac arrest event that is reversed, usually by cardiopulmonary resuscitation (CPR), defibrillation, cardioversion, or cardiac pacing, with restoration of spontaneous circulation .

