1.2 MeSH Check Tags

- Humans
- Adult
- Middle Aged
- Aged
- Male
- Female
- Prospective Studies
- Cohort Studies
- Multicenter Studies
- Observational Studies

2. Basic Study Information

Item	Content
Study Title	Study on Risk Early Warning of Clinical Prediction Model Based on MultiParameter Stress Perfusion Cardiac Magnetic Resonance in Adverse Prognosis of Dilated Cardiomyopathy
Study Type	Observational, Prospective, Multicenter Cohort Study
Study Design	Prospective observational cohort study; focusing on evaluating the predictive value of myocardial microvascular dysfunction (MVD) assessed by stress perfusion cardiac magnetic resonance (CMR) for SCD-related events (primary endpoint) and secondary endpoint events in patients with DCM; artificial intelligence (AI) will be briefly used for auxiliary analysis of CMR image features without detailed model development and validation procedures.
Sample Size	Planned enrollment of ≥ 450 patients with DCM (recruited from three study centers) to ensure sufficient statistical power for analyzing the correlation between MVD and SCD-related events.
Study Duration	Total study duration: 36 months (3 months of

	preparation, 9 months of recruitment and baseline assessment, 24 months of follow-up, 6 months of data analysis and report writing)
Follow-up Period	24 months after baseline stress perfusion CMR examination; additional 6 months of follow-up after the occurrence of the primary endpoint event; scheduled follow-up time points: 3 months, 6 months, 12 months, 18 months, 24 months post-CMR, and 1 year, 3 years, 5 years post-CMR for long-term outcome observation.
Primary Endpoint	A composite of SCD-related events, encompassing sudden cardiac death (SCD), appropriate implantable cardioverter-defibrillator (ICD) shock, and resuscitated cardiac arrest (see Appendix S1 for detailed diagnostic criteria) .
Secondary Endpoint	A composite of heart failure–related death, heart transplant, and left ventricle (LV) assist device implantation. Detailed definitions: heart failure-related death refers to death associated with clinically worsening heart failure symptoms without evidence of other causes; LV assist device implantation follows FDA-approved indications for mechanical circulatory support in severe heart failure patients .

Registration Information	Planned to be registered on ClinicalTrials.gov (NCT number to be assigned)

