6.3 Follow-up

1. **Follow-up Frequency and Time Points:** Follow-up will be conducted at 3 months, 6 months, 12 months, 18 months, and 24 months after baseline stress perfusion CMR examination. For subjects who experience the primary or secondary endpoint event, additional follow-up will be conducted for 6 months to record the recovery and long-term prognosis after the event. In addition, long-term follow-up will be conducted at 1 year, 3 years, and 5 years post-CMR to observe long-term outcomes.
2. **Follow-up Methods:** A combination of outpatient follow-up, telephone follow-up, and medical record review will be used. At each follow-up, researchers will record the occurrence of endpoint events (in detail for SCD-related events and secondary endpoint events), changes in clinical symptoms, medication adjustments, re-examination results (NT-proBNP, electrocardiogram, and CMR re-examination if necessary), and adverse events. For subjects with MVD at baseline, changes in MVD severity will be assessed by stress perfusion CMR re-examination at 12 and 24 months if clinically feasible.
3. **Endpoint Event Judgment:** An endpoint event judgment committee composed of 3 senior cardiologists will be established to review and confirm the occurrence of endpoint events. The committee will make a judgment based on medical records, examination results, and follow-up records, referring to the diagnostic criteria in Appendix S1 for SCD-related events, to ensure the accuracy and objectivity of the data. For SCD, the definition is death due to cardiac causes occurring within 1 hour of symptom onset with sudden loss of consciousness; for

appropriate ICD shock, it refers to shocks delivered in response to hemodynamically unstable ventricular tachycardia or fibrillation without reversible causes ; for resuscitated cardiac arrest, it refers to a cardiac arrest event reversed by cardiopulmonary resuscitation, defibrillation, or pacing .

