Statistical analysis will be performed using SPSS 26.0 and R software (version 4.2.0). Measurement data will be expressed as mean \pm standard deviation (SD) if normally distributed, or median (interquartile range, IQR) if abnormally distributed; comparison between groups will be performed using t-test, non-parametric test (Mann-Whitney U test, Kruskal-Wallis test) as appropriate. Count data will be expressed as rate (%) and compared using χ^2 test or Fisher's exact test. The Kaplan-Meier method will be used to draw the survival curve of subjects (for endpoint events), and the log-rank test will be used to compare the event rate between DCM patients with and without MVD. Multivariate Cox proportional hazards regression model will be used to screen the independent risk factors for SCD-related events and secondary endpoint events, with MVD (assessed by stress perfusion CMR) as the key independent variable. The receiver operating characteristic (ROC) curve will be used to evaluate the predictive efficacy of MVD for SCD-related events, and the AUC value will be calculated. $P < 0.05$ will be considered statistically significant. Subgroup analysis will be performed based on age, gender, LVEF, and MVD severity to explore the predictive value of MVD in different subgroups.

11. Study Schedule

Study Stage	Time Arrangement (Months)	Key Tasks
Preparation Stage	1–3	Finalize the study protocol, train researchers and related personnel (focusing on stress perfusion CMR scanning and MVD assessment), standardize CMR scanning parameters, establish the data management system, design Appendix S1 (diagnostic criteria for SCD-related events), and obtain ethical approval from each research center.

Recruitment and Baseline Assessment Stage	4–12	Recruit subjects, conduct baseline assessment (clinical data collection, laboratory tests, electrocardiogram, stress perfusion CMR examination), review inclusion/exclusion criteria, assess MVD using stress perfusion CMR (with brief AI auxiliary analysis), and complete data entry and verification.
Follow-up Stage	13–36	Conduct regular follow-up, record endpoint events and adverse events, perform stress perfusion CMR re-examination at 12 and 24 months (if feasible) to assess changes in MVD severity, update study data, and conduct long-term follow-up at 1 year, 3 years, and 5 years post-CMR.

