Data Analysis and Report Writing Stage	31–36	Conduct statistical analysis of the study data (focusing on the correlation between MVD and SCD-related events), sort out the study results, write the study report and Appendix S1, and submit the report to the Ethics Committee and relevant departments.

12. Adverse Event Management

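### The status, time limit and precedence of probable SCD in the primary endpoint are not settled, the schedule leaves room to revise its criteria late, and no masking of the endpoint committee to MVD is stated

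*Protocol*

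**What the plan says.** Section 2 makes SCD one of three components of the primary composite and points to Appendix S1 for the criteria. Section 6.3, item 3, has the committee decide "referring to the diagnostic criteria in Appendix S1 for SCD-related events" and then gives its own statement: "For SCD, the definition is death due to cardiac causes occurring within 1 hour of symptom onset with sudden loss of consciousness".

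Appendix S1, item 1, opens with the same rule: "Death due to cardiac causes occurring within 1 hour of the onset of acute cardiac symptoms, characterized by sudden loss of consciousness". It then adds a category that Section 6.3 does not mention: "For unwitnessed deaths with clear evidence of cardiac etiology, it is classified as probable SCD".

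The secondary composite in Section 2 has its own fatal component: "heart failure-related death refers to death associated with clinically worsening heart failure symptoms without evidence of other causes".

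Section 11 names the appendix twice. In months 1–3 the task is to "design Appendix S1 (diagnostic criteria for SCD-related events"; in months 31–36, the data analysis stage, it is to "write the study report and Appendix S1".

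On the evidence used, Section 6.3 says: "The committee will make a judgment based on medical records, examination results, and follow-up records". Nothing in the protocol says whether stress perfusion results are shown to the committee or withheld.

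**The concern.** An unwitnessed death can rarely be shown to meet a 1-hour rule, so its place in the primary endpoint depends on what probable SCD means. If it counts without a time limit, cardiac deaths that were not sudden can enter the primary endpoint. If it does not count, true sudden deaths at home or during sleep are lost. Section 10 plans a Cox model for each endpoint, so a death moved between the two changes both.

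The other two matters make this worse. If the criteria can be reworded during analysis, the rule may be settled by people who already know which deaths occurred in patients with MVD. If the committee can see MVD status while deciding between sudden and heart failure death, the decision may lean towards the study hypothesis. That error would be related to exposure, so it could bias the primary hazard ratio as well as blur it.

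**Working it through.** The protocol gives no figure to reproduce here, so most of the check is a comparison of its texts.

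**1. The definition.**

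| Question | Section 6.3 | Appendix S1 |
|---|---|---|
| 1-hour rule | Yes | Yes, same rule |
| Unwitnessed death | Not mentioned | Probable SCD, if a cardiac cause is clear |
| Limit on time since last seen alive | None | None |
| Does probable SCD count in the primary composite? | Not stated | Not stated |
| Precedence against heart failure-related death | Not stated | Not stated |

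The two places agree on the 1-hour rule, and Section 6.3 defers to the appendix. Section 6.3 is therefore an incomplete restatement, and the appendix leaves open the status of the category it adds.

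**2. The overlap.** Take a patient whose heart failure has been worsening and who is found dead with no other cause apparent. A cardiac cause is clear, so Appendix S1 allows probable SCD. The death followed worsening symptoms with no other cause in evidence, so Section 2 allows heart failure-related death. No rule says which comes first.

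**3. The schedule.** Recruitment starts in month 4 and the analysis stage in month 31. Events can therefore accrue over months 4 to 30, which is 30 − 4 + 1 = 27 months, before the second entry for Appendix S1 is reached.

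**4. What the committee can see.** The three listed sources can each carry MVD status:
- Test results: the baseline stress CMR is a study examination (Section 6.2).
- Follow-up records: these include CMR re-examination. Section 6.3 plans repeat stress CMR at 12 and 24 months for subjects with baseline MVD, so a scheduled repeat scan on file can itself disclose exposure.
- Medical records: Section 9, item 3, has researchers tell treating physicians about high-risk subjects, especially those with severe MVD.

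**5. Illustrative size, definition issue only.** From the protocol: 450 patients and 24 months. Assumed: 3% of patients per year with a primary event, half of the events being deaths, and 30% to 50% of those deaths unwitnessed and eligible as probable SCD.
- Events: 450 × (1 − exp(−0.03 × 2)) = 450 × 0.0582 = 26.2, about 26.
- Deaths among them: 26 × 0.5 = 13.
- Unwitnessed: 13 × 0.3 = 3.9 to 13 × 0.5 = 6.5, that is 4 to 7 events.
- Share of the endpoint: 0.5 × 0.3 = 15% to 0.5 × 0.5 = 25%.

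The share does not depend on the assumed event rate. It depends only on the two assumed proportions.

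**The case against.** The best defence is that the protocol has one governing text. Both Section 2 and Section 6.3 send the reader to Appendix S1, and the 1-hour rule is identical. A reader might infer two rival definitions of SCD, but the documents do not support that. The probable SCD sentence also sits under the SCD item of an appendix on SCD-related events, so the natural reading is that it counts. That reading is reasonable, but it is not stated, and it supplies no time limit.

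The overlap is partly handled: the heart failure definition excludes deaths with evidence of another cause, the appendix asks for clear evidence, and one committee judges both endpoints. What remains is the death in which heart failure is itself the cardiac cause.

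On timing, a reader might infer that the endpoint criteria are first set during analysis. They are not. They are designed before recruitment and already appear in the protocol, and the late entry may mean only writing the appendix up with the report. The point that stands is that the two entries need reconciling, because as worded they leave room for revision.

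On masking, a reader might infer that the committee file is stated to contain the MVD result. No text says so. It is a strong inference from the listed sources, and a committee charter that is not shown may deal with it. Even so, the protocol itself names the evidence the committee uses and gives no limit on it.

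**Conclusion.** The concern holds in this bounded form. Section 6.3 restates the SCD definition incompletely. Appendix S1 adds an unwitnessed category with no time limit, no express status in the primary composite and no precedence against heart failure-related death. Followed as written, the text can class cardiac deaths that were not sudden as primary events. The two schedule entries leave room for late revision, and no masking to MVD is stated although the sources would be expected to reveal it.

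The gap in the definition, the double entry and the silence on masking are plain from the text. That the criteria would in fact be revised, or that the committee would in fact lean one way, is not shown. The 15% to 25% figure is an illustration on assumed rates. It covers only the definition issue and says nothing about the size of any bias from the schedule or from unmasked judgment. The matter should be settled before the first death is judged, because impartial reclassification is harder afterwards.

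**What to change.** - Put one SCD definition in Section 6.3 and Appendix S1, or have Section 6.3 refer to the appendix without restating it.
- State whether probable SCD counts in the primary endpoint. If it does, add a last-seen-alive-and-stable limit chosen by the sponsor.
- Add precedence rules that make SCD, including probable SCD, and heart failure-related death mutually exclusive.
- Fix Appendix S1 before the first patient is enrolled, and delete the mention of it from the months 31–36 entry in Section 11.
- State that committee files are stripped of all baseline and repeat perfusion, MPR and MVD results, and of any notice to physicians that mentions them. Removing the baseline report alone would not mask the committee, because repeat scans and notices can also disclose MVD.

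The cost is protocol wording and a small redaction workload for each event file.
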